Dead	N (xx.x%)	N (xx.x%)	xx.x (xx.x to xx.x)	xx.x (xx.x to xx.x)	x.xxx
Secondary outcomes using phenotype allocation defined by the complete dataset using latent class analysis					
Time to extubation ^b	xx.x (xx.x)	xx.x (xx.x)	xx.x (xx.x to xx.x)		x.xxx
Intubation rate ^a	N (xx.x%)	N (xx.x%)	xx.x (xx.x to xx.x)		x.xxx
Re-intubation rate ^a	N (xx.x%)	N (xx.x%)	xx.x (xx.x to xx.x)		x.xxx
Ventilator free days at day 28 ^b	xx.x (xx.x)	xx.x (xx.x)	xx.x (xx.x to xx.x)		x.xxx
Duration of ventilation ^b	xx.x (xx.x)	xx.x (xx.x)	xx.x (xx.x to xx.x)		x.xxx
Length of ICU stay ^c	xx.x [xx.x, xx.x]	xx.x [xx.x, xx.x]			x.xxx
Length of hospital stay ^c	xx.x [xx.x, xx.x]	xx.x [xx.x, xx.x]			x.xxx
28-day mortality ^a					
Alive	N (xx.x%)	N (xx.x%)	xx.x (xx.x to xx.x)		
Dead	N (xx.x%)	N (xx.x%)	xx.x (xx.x to xx.x)	xx.x (xx.x to xx.x)	x.xxx

No. (%) for phenotypes and mean difference and risk ratio (95% CI) presented.

Unadjusted p-value from chi-square.

Table x.x.x Sensitivity analysis of the main clinical outcomes, patients receiving high-flow nasal oxygen

	Hyper-inflammatory phenotype n = (%)	Hypo-inflammatory phenotype n = (%)	Unadjusted % Point or Mean Difference (95% CI)	Unadjusted risk ratio (95% CI)	p-value	Adjusted odds ratio (95% CI)	p-value
Primary outcome ^a							
Mortality at 60 days in patients with ARDS as defined by the POC assay							
Alive	N (xx.x%)	N (xx.x%)	xx.x (xx.x to xx.x)				
Dead	N (xx.x%)	N (xx.x%)	xx.x (xx.x to xx.x)	xx.x (xx.x to xx.x)	x.xxx		
Secondary outcomes							
Adjusted 60-day mortality (phenotype defined by POC assay)						xx.x (xx.x to xx.x)	x.xxx
Intubation rate^a	N (xx.x%)	N (xx.x%)	xx.x (xx.x to xx.x)		x.xxx		x.xxx
Ventilator free days at day 28 ^b	xx.x (xx.x)	xx.x (xx.x)	xx.x (xx.x to xx.x)		x.xxx		x.xxx
Duration of ventilation ^b	xx.x (xx.x)	xx.x (xx.x)	xx.x (xx.x to xx.x)		x.xxx		x.xxx
Length of ICU stay ^c	xx.x [xx.x, xx.x]	xx.x [xx.x, xx.x]			x.xxx		
Length of hospital stay ^c	xx.x [xx.x, xx.x]	xx.x [xx.x, xx.x]			x.xxx		
28-day mortality ^a							
Alive	N (xx.x%)	N (xx.x%)	xx.x (xx.x to xx.x)				
Dead	N (xx.x%)	N (xx.x%)	xx.x (xx.x to xx.x)	xx.x (xx.x to xx.x)	x.xxx	xx.x (xx.x to xx.x)	x.xxx

^a No. (%) for phenotypes and mean difference and risk ratio (95% CI) presented and unadjusted p-value from chi-square and adjusted p-value from logistic regression adjusted for age, gender, and site.

^b Mean(SD) for phenotypes and mean difference (95% CI) presented, unadjusted.

^c Median[IQR] and p-value from Mann-Whitney test.

Table x.x.x Secondary analyses, high flow nasal oxygen cohort

	Hyper-inflammatory phenotype n = (%)	Hypo-inflammatory phenotype n = (%)	Unadjusted % Point or Mean Difference (95% CI)	Unadjusted Risk ratio (95% CI)	p-value
Mortality at 60 days in patients with ARDS defined by the standard laboratory assays and parsimonious model					
Alive	N (xx.x%)	N (xx.x%)	xx.x (xx.x to xx.x)		
Dead	N (xx.x%)	N (xx.x%)	xx.x (xx.x to xx.x)	xx.x (xx.x to xx.x)	x.xxx
Mortality at 60 days in patients with ARDS defined by the complete data-set using latent class analysis					
Alive	N (xx.x%)	N (xx.x%)	xx.x (xx.x to xx.x)		
Dead	N (xx.x%)	N (xx.x%)	xx.x (xx.x to xx.x)	xx.x (xx.x to xx.x)	x.xxx
Secondary outcomes using phenotype allocation defined by the complete dataset using latent class analysis					
Intubation rate ^a	N (xx.x%)	N (xx.x%)	xx.x (xx.x to xx.x)		x.xxx
Ventilator free days at day 28 ^b	xx.x (xx.x)	xx.x (xx.x)	xx.x (xx.x to xx.x)		x.xxx
Duration of ventilation ^b	xx.x (xx.x)	xx.x (xx.x)	xx.x (xx.x to xx.x)		x.xxx
Length of ICU stay ^c	xx.x [xx.x, xx.x]	xx.x [xx.x, xx.x]			x.xxx
Length of hospital stay ^c	xx.x [xx.x, xx.x]	xx.x [xx.x, xx.x]			x.xxx
28-day mortality ^a					
Alive	N (xx.x%)	N (xx.x%)	xx.x (xx.x to xx.x)		
Dead	N (xx.x%)	N (xx.x%)	xx.x (xx.x to xx.x)	xx.x (xx.x to xx.x)	x.xxx

No. (%) for phenotypes and mean difference and risk ratio (95% CI) presented.

Unadjusted p-value from chi-square.

Table x.x.x Sensitivity analysis of the main clinical outcomes, patients receiving high-flow nasal oxygen at a rate of at least 30 litres per minute

	Hyper-inflammatory phenotype n = (%)	Hypo-inflammatory phenotype n = (%)	Unadjusted % Point or Mean Difference (95% CI)	Unadjusted risk ratio (95% CI)	p-value	Adjusted odds ratio (95% CI)	p-value
Primary outcome ^a							
Mortality at 60 days in patients with ARDS as defined by the POC assay							
Alive	N (xx.x%)	N (xx.x%)	xx.x (xx.x to xx.x)				
Dead	N (xx.x%)	N (xx.x%)	xx.x (xx.x to xx.x)	xx.x (xx.x to xx.x)	x.xxx		
Secondary outcomes							
Adjusted 60-day mortality (phenotype defined by POC assay)						xx.x (xx.x to xx.x)	x.xxx
Time to extubation ^b	xx.x (xx.x)	xx.x (xx.x)	xx.x (xx.x to xx.x)		x.xxx		x.xxx
Intubation rate^a	N (xx.x%)	N (xx.x%)	xx.x (xx.x to xx.x)		x.xxx		x.xxx
Ventilator free days at day 28 ^b	xx.x (xx.x)	xx.x (xx.x)	xx.x (xx.x to xx.x)		x.xxx		x.xxx
Duration of ventilation ^b	xx.x (xx.x)	xx.x (xx.x)	xx.x (xx.x to xx.x)		x.xxx		x.xxx
Length of ICU stay ^c	xx.x [xx.x, xx.x]	xx.x [xx.x, xx.x]			x.xxx		
Length of hospital stay ^c	xx.x [xx.x, xx.x]	xx.x [xx.x, xx.x]			x.xxx		
28-day mortality ^a							
Alive	N (xx.x%)	N (xx.x%)	xx.x (xx.x to xx.x)				
Dead	N (xx.x%)	N (xx.x%)	xx.x (xx.x to xx.x)	xx.x (xx.x to xx.x)	x.xxx	xx.x (xx.x to xx.x)	x.xxx

^a No. (%) for phenotypes and mean difference and risk ratio (95% CI) presented and unadjusted p-value from chi-square and adjusted p-value from logistic regression adjusted for age, gender, and site.

^b Mean(SD) for phenotypes and mean difference (95% CI) presented, unadjusted.

^c Median[IQR] and p-value from Mann-Whitney test.

Table x.x.x Secondary analyses, high flow nasal oxygen (≥ 30 litres per minute) cohort

	Hyper-inflammatory phenotype n = (%)	Hypo-inflammatory phenotype n = (%)	Unadjusted % Point or Mean Difference (95% CI)	Unadjusted Risk ratio (95% CI)	p-value
Mortality at 60 days in patients with ARDS defined by the standard laboratory assays and parsimonious model					
Alive	N (xx.x%)	N (xx.x%)	xx.x (xx.x to xx.x)		
Dead	N (xx.x%)	N (xx.x%)	xx.x (xx.x to xx.x)	xx.x (xx.x to xx.x)	x.xxx
Mortality at 60 days in patients with ARDS defined by the complete data-set using latent class analysis					
Alive	N (xx.x%)	N (xx.x%)	xx.x (xx.x to xx.x)		
Dead	N (xx.x%)	N (xx.x%)	xx.x (xx.x to xx.x)	xx.x (xx.x to xx.x)	x.xxx
Secondary outcomes using phenotype allocation defined by the complete dataset using latent class analysis					
Intubation rate ^a	N (xx.x%)	N (xx.x%)	xx.x (xx.x to xx.x)		x.xxx
Ventilator free days at day 28 ^b	xx.x (xx.x)	xx.x (xx.x)	xx.x (xx.x to xx.x)		x.xxx
Duration of ventilation ^b	xx.x (xx.x)	xx.x (xx.x)	xx.x (xx.x to xx.x)		x.xxx
Length of ICU stay ^c	xx.x [xx.x, xx.x]	xx.x [xx.x, xx.x]			x.xxx
Length of hospital stay ^c	xx.x [xx.x, xx.x]	xx.x [xx.x, xx.x]			x.xxx
28-day mortality ^a					
Alive	N (xx.x%)	N (xx.x%)	xx.x (xx.x to xx.x)		
Dead	N (xx.x%)	N (xx.x%)	xx.x (xx.x to xx.x)	xx.x (xx.x to xx.x)	x.xxx

No. (%) for phenotypes and mean difference and risk ratio (95% CI) presented.
Unadjusted p-value from chi-square.

Table x.x.x Sensitivity analysis of the main clinical outcome variables, cohort excluding COVID-19 patients

	Hyper-inflammatory phenotype n = (%)	Hypo-inflammatory phenotype n = (%)	Unadjusted % Point or Mean Difference (95% CI)	Unadjusted risk ratio (95% CI)	p-value	Adjusted odds ratio (95% CI)	p-value
Primary outcome ^a							
Mortality at 60 days in patients with ARDS as defined by the POC assay							
Alive	N (xx.x%)	N (xx.x%)	xx.x (xx.x to xx.x)				
Dead	N (xx.x%)	N (xx.x%)	xx.x (xx.x to xx.x)	xx.x (xx.x to xx.x)	x.xxx		
Secondary outcomes							
Adjusted 60-day mortality (phenotype defined by POC assay)						xx.x (xx.x to xx.x)	x.xxx
Time to extubation ^b	xx.x (xx.x)	xx.x (xx.x)	xx.x (xx.x to xx.x)		x.xxx		x.xxx
Intubation rate^a	N (xx.x%)	N (xx.x%)	xx.x (xx.x to xx.x)		x.xxx		x.xxx
Re-intubation rate ^a	N (xx.x%)	N (xx.x%)	xx.x (xx.x to xx.x)		x.xxx		x.xxx
Ventilator free days at day 28 ^b	xx.x (xx.x)	xx.x (xx.x)	xx.x (xx.x to xx.x)		x.xxx		x.xxx
Duration of ventilation ^b	xx.x (xx.x)	xx.x (xx.x)	xx.x (xx.x to xx.x)		x.xxx		x.xxx
Length of ICU stay ^c	xx.x [xx.x, xx.x]	xx.x [xx.x, xx.x]			x.xxx		
Length of hospital stay ^c	xx.x [xx.x, xx.x]	xx.x [xx.x, xx.x]			x.xxx		
28-day mortality ^a							
Alive	N (xx.x%)	N (xx.x%)	xx.x (xx.x to xx.x)				
Dead	N (xx.x%)	N (xx.x%)	xx.x (xx.x to xx.x)	xx.x (xx.x to xx.x)	x.xxx	xx.x (xx.x to xx.x)	x.xxx

^a No. (%) for phenotypes and mean difference and risk ratio (95% CI) presented and unadjusted p-value from chi-square and adjusted p-value from logistic regression adjusted for age, gender, and site.

^b Mean(SD) for phenotypes and mean difference (95% CI) presented, unadjusted.

^c Median[IQR] and p-value from Mann-Whitney test.

Table x.x.x Secondary analyses, cohort excluding COVID-19 patients

	Hyper-inflammatory phenotype n = (%)	Hypo-inflammatory phenotype n = (%)	Unadjusted % Point or Mean Difference (95% CI)	Unadjusted Risk ratio (95% CI)	p-value
Mortality at 60 days in patients with ARDS defined by commercially-available assays and parsimonious model					
Alive	N (xx.x%)	N (xx.x%)	xx.x (xx.x to xx.x)		
Dead	N (xx.x%)	N (xx.x%)	xx.x (xx.x to xx.x)	xx.x (xx.x to xx.x)	x.xxx
Mortality at 60 days in patients with ARDS defined by the complete data-set using latent class analysis					
Alive	N (xx.x%)	N (xx.x%)	xx.x (xx.x to xx.x)		
Dead	N (xx.x%)	N (xx.x%)	xx.x (xx.x to xx.x)	xx.x (xx.x to xx.x)	x.xxx
Secondary outcomes using phenotype allocation defined by the complete dataset using latent class analysis					
Time to extubation^b	xx.x (xx.x)	xx.x (xx.x)	xx.x (xx.x to xx.x)		x.xxx
Intubation rate^a	N (xx.x%)	N (xx.x%)	xx.x (xx.x to xx.x)		x.xxx
Re-intubation rate^a	N (xx.x%)	N (xx.x%)	xx.x (xx.x to xx.x)		x.xxx
Ventilator free days at day 28^b	xx.x (xx.x)	xx.x (xx.x)	xx.x (xx.x to xx.x)		x.xxx
Duration of ventilation^b	xx.x (xx.x)	xx.x (xx.x)	xx.x (xx.x to xx.x)		x.xxx
Length of ICU stay^c	xx.x [xx.x, xx.x]	xx.x [xx.x, xx.x]			x.xxx
Length of hospital stay^c	xx.x [xx.x, xx.x]	xx.x [xx.x, xx.x]			x.xxx
28-day mortality^a					
Alive	N (xx.x%)	N (xx.x%)	xx.x (xx.x to xx.x)		
Dead	N (xx.x%)	N (xx.x%)	xx.x (xx.x to xx.x)	xx.x (xx.x to xx.x)	x.xxx

No. (%) for phenotypes and mean difference and risk ratio (95% CI) presented.

Unadjusted p-value from chi-square.

Table x.x.x Sensitivity analysis of the main clinical outcome variables, cohort restricted to patients with biosamples obtained within 24 hours of ARDS diagnosis

	Hyper-inflammatory phenotype n = (%)	Hypo-inflammatory phenotype n = (%)	Unadjusted % Point or Mean Difference (95% CI)	Unadjusted risk ratio (95% CI)	p-value	Adjusted odds ratio (95% CI)	p-value
Primary outcome ^a							
Mortality at 60 days in patients with ARDS as defined by the POC assay							
Alive	N (xx.x%)	N (xx.x%)	xx.x (xx.x to xx.x)				
Dead	N (xx.x%)	N (xx.x%)	xx.x (xx.x to xx.x)	xx.x (xx.x to xx.x)	x.xxx		
Secondary outcomes							
Adjusted 60-day mortality (phenotype defined by POC assay)						xx.x (xx.x to xx.x)	x.xxx
Time to extubation ^b	xx.x (xx.x)	xx.x (xx.x)	xx.x (xx.x to xx.x)		x.xxx		x.xxx
Intubation rate^a	N (xx.x%)	N (xx.x%)	xx.x (xx.x to xx.x)		x.xxx		x.xxx
Re-intubation rate ^a	N (xx.x%)	N (xx.x%)	xx.x (xx.x to xx.x)		x.xxx		x.xxx
Ventilator free days at day 28 ^b	xx.x (xx.x)	xx.x (xx.x)	xx.x (xx.x to xx.x)		x.xxx		x.xxx
Duration of ventilation ^b	xx.x (xx.x)	xx.x (xx.x)	xx.x (xx.x to xx.x)		x.xxx		x.xxx
Length of ICU stay ^c	xx.x [xx.x, xx.x]	xx.x [xx.x, xx.x]			x.xxx		
Length of hospital stay ^c	xx.x [xx.x, xx.x]	xx.x [xx.x, xx.x]			x.xxx		
28-day mortality ^a							
Alive	N (xx.x%)	N (xx.x%)	xx.x (xx.x to xx.x)				
Dead	N (xx.x%)	N (xx.x%)	xx.x (xx.x to xx.x)	xx.x (xx.x to xx.x)	x.xxx	xx.x (xx.x to xx.x)	x.xxx

^a No. (%) for phenotypes and mean difference and risk ratio (95% CI) presented and unadjusted p-value from chi-square and adjusted p-value from logistic regression adjusted for age, gender, and site.

^b Mean(SD) for phenotypes and mean difference (95% CI) presented, unadjusted.

^c Median[IQR] and p-value from Mann-Whitney test.

Table x.x.x Secondary analyses, cohort restricted to patients with biosamples obtained within 24 hours of ARDS diagnosis

	Hyper-inflammatory phenotype n = (%)	Hypo-inflammatory phenotype n = (%)	Unadjusted % Point or Mean Difference (95% CI)	Unadjusted Risk ratio (95% CI)	p-value
Mortality at 60 days in patients with ARDS defined by commercially-available assays and parsimonious model					
Alive	N (xx.x%)	N (xx.x%)	xx.x (xx.x to xx.x)		
Dead	N (xx.x%)	N (xx.x%)	xx.x (xx.x to xx.x)	xx.x (xx.x to xx.x)	x.xxx
Mortality at 60 days in patients with ARDS defined by the complete data-set using latent class analysis					
Alive	N (xx.x%)	N (xx.x%)	xx.x (xx.x to xx.x)		
Dead	N (xx.x%)	N (xx.x%)	xx.x (xx.x to xx.x)	xx.x (xx.x to xx.x)	x.xxx
Secondary outcomes using phenotype allocation defined by the complete dataset using latent class analysis					
Time to extubation^b	xx.x (xx.x)	xx.x (xx.x)	xx.x (xx.x to xx.x)		x.xxx
Intubation rate^a	N (xx.x%)	N (xx.x%)	xx.x (xx.x to xx.x)		x.xxx
Re-intubation rate^a	N (xx.x%)	N (xx.x%)	xx.x (xx.x to xx.x)		x.xxx
Ventilator free days at day 28^b	xx.x (xx.x)	xx.x (xx.x)	xx.x (xx.x to xx.x)		x.xxx
Duration of ventilation^b	xx.x (xx.x)	xx.x (xx.x)	xx.x (xx.x to xx.x)		x.xxx
Length of ICU stay^c	xx.x [xx.x, xx.x]	xx.x [xx.x, xx.x]			x.xxx
Length of hospital stay^c	xx.x [xx.x, xx.x]	xx.x [xx.x, xx.x]			x.xxx
28-day mortality^a					
Alive	N (xx.x%)	N (xx.x%)	xx.x (xx.x to xx.x)		
Dead	N (xx.x%)	N (xx.x%)	xx.x (xx.x to xx.x)	xx.x (xx.x to xx.x)	x.xxx

No. (%) for phenotypes and mean difference and risk ratio (95% CI) presented.

Unadjusted p-value from chi-square.

Table x.x.x Sensitivity analysis of the main clinical outcome variables, cohort restricted to patients with biosamples obtained within 48 hours of ARDS diagnosis

	Hyper-inflammatory phenotype n = (%)	Hypo-inflammatory phenotype n = (%)	Unadjusted % Point or Mean Difference (95% CI)	Unadjusted risk ratio (95% CI)	p-value	Adjusted odds ratio (95% CI)	p-value
Primary outcome ^a							
Mortality at 60 days in patients with ARDS as defined by the POC assay							
Alive	N (xx.x%)	N (xx.x%)	xx.x (xx.x to xx.x)				
Dead	N (xx.x%)	N (xx.x%)	xx.x (xx.x to xx.x)	xx.x (xx.x to xx.x)	x.xxx		
Secondary outcomes							
Adjusted 60-day mortality (phenotype defined by POC assay)						xx.x (xx.x to xx.x)	x.xxx
Time to extubation ^b	xx.x (xx.x)	xx.x (xx.x)	xx.x (xx.x to xx.x)		x.xxx		x.xxx
Intubation rate^a	N (xx.x%)	N (xx.x%)	xx.x (xx.x to xx.x)		x.xxx		x.xxx
Re-intubation rate ^a	N (xx.x%)	N (xx.x%)	xx.x (xx.x to xx.x)		x.xxx		x.xxx
Ventilator free days at day 28 ^b	xx.x (xx.x)	xx.x (xx.x)	xx.x (xx.x to xx.x)		x.xxx		x.xxx
Duration of ventilation ^b	xx.x (xx.x)	xx.x (xx.x)	xx.x (xx.x to xx.x)		x.xxx		x.xxx
Length of ICU stay ^c	xx.x [xx.x, xx.x]	xx.x [xx.x, xx.x]			x.xxx		
Length of hospital stay ^c	xx.x [xx.x, xx.x]	xx.x [xx.x, xx.x]			x.xxx		
28-day mortality ^a							
Alive	N (xx.x%)	N (xx.x%)	xx.x (xx.x to xx.x)				
Dead	N (xx.x%)	N (xx.x%)	xx.x (xx.x to xx.x)	xx.x (xx.x to xx.x)	x.xxx	xx.x (xx.x to xx.x)	x.xxx

^a No. (%) for phenotypes and mean difference and risk ratio (95% CI) presented and unadjusted p-value from chi-square and adjusted p-value from logistic regression adjusted for age, gender, and site.

^b Mean(SD) for phenotypes and mean difference (95% CI) presented, unadjusted.

^c Median[IQR] and p-value from Mann-Whitney test.

Table x.x.x Secondary analyses, cohort restricted to patients with biosamples obtained within 48 hours of ARDS diagnosis

	Hyper-inflammatory phenotype n = (%)	Hypo-inflammatory phenotype n = (%)	Unadjusted % Point or Mean Difference (95% CI)	Unadjusted Risk ratio (95% CI)	p-value
Mortality at 60 days in patients with ARDS defined by commercially-available assays and parsimonious model					
Alive	N (xx.x%)	N (xx.x%)	xx.x (xx.x to xx.x)		
Dead	N (xx.x%)	N (xx.x%)	xx.x (xx.x to xx.x)	xx.x (xx.x to xx.x)	x.xxx
Mortality at 60 days in patients with ARDS defined by the complete data-set using latent class analysis					
Alive	N (xx.x%)	N (xx.x%)	xx.x (xx.x to xx.x)		
Dead	N (xx.x%)	N (xx.x%)	xx.x (xx.x to xx.x)	xx.x (xx.x to xx.x)	x.xxx
Secondary outcomes using phenotype allocation defined by the complete dataset using latent class analysis					
Time to extubation ^b	xx.x (xx.x)	xx.x (xx.x)	xx.x (xx.x to xx.x)		x.xxx
Intubation rate ^a	N (xx.x%)	N (xx.x%)	xx.x (xx.x to xx.x)		x.xxx
Re-intubation rate ^a	N (xx.x%)	N (xx.x%)	xx.x (xx.x to xx.x)		x.xxx
Ventilator free days at day 28 ^b	xx.x (xx.x)	xx.x (xx.x)	xx.x (xx.x to xx.x)		x.xxx
Duration of ventilation ^b	xx.x (xx.x)	xx.x (xx.x)	xx.x (xx.x to xx.x)		x.xxx
Length of ICU stay ^c	xx.x [xx.x, xx.x]	xx.x [xx.x, xx.x]			x.xxx
Length of hospital stay ^c	xx.x [xx.x, xx.x]	xx.x [xx.x, xx.x]			x.xxx
28-day mortality ^a					
Alive	N (xx.x%)	N (xx.x%)	xx.x (xx.x to xx.x)		
Dead	N (xx.x%)	N (xx.x%)	xx.x (xx.x to xx.x)	xx.x (xx.x to xx.x)	x.xxx

No. (%) for phenotypes and mean difference and risk ratio (95% CI) presented.
Unadjusted p-value from chi-square.

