Duration of ventilation (days)	From the date of commencing ventilatory support, or the date of ICU admission, if the patient was receiving ventilatory support prior to ICU admission, to the time of initiating unassisted breathing.

	
Duration of ventilation
 
Date of unassisted breathing – Date of commencing ventilatory support, if the patient achieved unassisted breathing
 $= \begin{cases} \text{Date of death} - \text{Date of commencing ventilatory support, if the patient died prior to achieving unassisted breathing} \end{cases}$
Duration of ICU stay (days)	
Duration of critical care and hospital stay will be counted from ICU admission to discharge.
 
Duration of ICU stay
 
Date of first ICU discharge – Date of ICU admission, if the patient is alive at ICU discharge
 $= \begin{cases} \text{Date of death} - \text{Date of ICU admission, if the patient died prior to ICU discharge} \end{cases}$
Duration of hospital stay (days)	
Duration of critical care and hospital stay will be counted from ICU admission to discharge.
 
Duration of hospital stay
 
Date of first hospital discharge – Date of ICU admission, if the patient is alive at hospital discharge
 $= \begin{cases} \text{Date of death} - \text{Date of ICU admission, if the patient died prior to hospital discharge} \end{cases}$ 
Hospital discharge is the first date that the patient is discharged to home/community, a transfer between hospitals is not considered as a hospital discharge.

Extubation	First time being successfully free from an endotracheal tube or a tracheostomy tube for 48 hours
Time to extubation	From date of intubation to extubation, or from the date of ICU admission to successful extubation, if the patient was intubated prior to ICU admission.

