8.5 Study Outcomes

Primary outcome:

- Mortality at 60 days in patients with ARDS as defined by the POC assay, reported as n (%) by phenotype, unadjusted percentage point difference (95% CI), risk ratio (95% CI), and p value from Pearson's chi-square test

Secondary outcomes:

- Mortality at 60 days in patients with ARDS as defined by the POC assay, reported as odds ratio (95% CI) and p value from adjusted logistic regression (adjusted for age and gender)
- Mortality at 60 days in patients with ARDS defined by commercially-available laboratory assays and parsimonious models, reported as n (%) by phenotype, unadjusted percentage point difference (95%, CI), risk ratio (95% CI), and p value from Pearson's chi-square test (95% CI).

- Mortality at 60 days in patients with ARDS defined by the complete data-set using latent class analysis, reported as n (%) by phenotype, unadjusted percentage point difference (95% CI), risk ratio (95% CI), and p value from Pearson's chi-square test (95% CI).

For further secondary analyses, the assumption of normal distribution will be checked graphically for each continuous variable, but we anticipate using the following tests (alternative in brackets).

- Time to extubation, mean (SD) by phenotype, difference in means (95% CI) and p value from two-sided t-test for unpaired data (Mann-Whitney test)
- Intubation rate in patients receiving HFNO, number (%) by phenotype, percentage point difference (95% CI), and p value from chi-square test
- Re-intubation rate, number (%) by phenotype, percentage point difference (95% CI), and p value from chi-square test
- Ventilator free days at day 28, mean (SD) by phenotype, difference in means (95% CI) and p value from t-test for unpaired data (Mann-Whitney test)
- Duration of ventilation, mean (SD) by phenotype, difference in means (95% CI) and p value from t-test for unpaired data (Mann-Whitney test)
- Length of ICU stay, median (IQR) by phenotype, p value from Mann-Whitney test
- Length of hospital stay, median (IQR) by phenotype, p value from Mann-Whitney test
- 28-day mortality, n (%) by phenotype, unadjusted percentage point difference (95% CI) and Risk ratio (95% CI) and p value from chi-square
- Time to extubation, difference in means (95% CI) adjusted for age, co-morbidity, aetiology of ARDS, vasopressor requirement and PF ratio. P-values will be from ANCOVA.

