Alive	N (xx.x%)	N (xx.x%)	xx.x (xx.x to xx.x)		
Dead	N (xx.x%)	N (xx.x%)	xx.x (xx.x to xx.x)	xx.x (xx.x to xx.x)	x.xxx

No. (%) for phenotypes and mean difference and risk ratio (95% CI) presented.

Unadjusted p-value from chi-square.

Table x.x.x Sensitivity analysis of the main clinical outcomes in patients receiving non-invasive ventilation

	Hyper-inflammatory phenotype n = (%)	Hypo-inflammatory phenotype n = (%)	Unadjusted % Point or Mean Difference (95% CI)	Unadjusted risk ratio (95% CI)	p-value	Adjusted odds ratio (95% CI)	p-value
Primary outcome ^a							
Mortality at 60 days in patients with ARDS as defined by the POC assay							
Alive	N (xx.x%)	N (xx.x%)	xx.x (xx.x to xx.x)				
Dead	N (xx.x%)	N (xx.x%)	xx.x (xx.x to xx.x)	xx.x (xx.x to xx.x)	x.xxx		
Secondary outcomes							
Adjusted 60-day mortality (phenotype defined by POC assay)						xx.x (xx.x to xx.x)	x.xxx
Intubation rate^a	N (xx.x%)	N (xx.x%)	xx.x (xx.x to xx.x)		x.xxx		x.xxx
Re-intubation rate ^a	N (xx.x%)	N (xx.x%)	xx.x (xx.x to xx.x)		x.xxx		x.xxx
Ventilator free days at day 28 ^b	xx.x (xx.x)	xx.x (xx.x)	xx.x (xx.x to xx.x)		x.xxx		x.xxx
Duration of ventilation ^b	xx.x (xx.x)	xx.x (xx.x)	xx.x (xx.x to xx.x)		x.xxx		x.xxx
Length of ICU stay ^c	xx.x [xx.x, xx.x]	xx.x [xx.x, xx.x]			x.xxx		
Length of hospital stay ^c	xx.x [xx.x, xx.x]	xx.x [xx.x, xx.x]			x.xxx		
28-day mortality ^a							
Alive	N (xx.x%)	N (xx.x%)	xx.x (xx.x to xx.x)				
Dead	N (xx.x%)	N (xx.x%)	xx.x (xx.x to xx.x)	xx.x (xx.x to xx.x)	x.xxx	xx.x (xx.x to xx.x)	x.xxx

^a No. (%) for phenotypes and mean difference and risk ratio (95% CI) presented and unadjusted p-value from chi-square and adjusted p-value from logistic regression adjusted for age, gender, and site.

^b Mean(SD) for phenotypes and mean difference (95% CI) presented, unadjusted.

^c Median[IQR] and p-value from Mann-Whitney test.

Table x.x.x Secondary analyses, non-invasive ventilation cohort

	Hyper-inflammatory phenotype n = (%)	Hypo-inflammatory phenotype n = (%)	Unadjusted % Point or Mean Difference (95% CI)	Unadjusted Risk ratio (95% CI)	p-value
Mortality at 60 days in patients with ARDS defined commercially-available assays and parsimonious model					
Alive	N (xx.x%)	N (xx.x%)	xx.x (xx.x to xx.x)		
Dead	N (xx.x%)	N (xx.x%)	xx.x (xx.x to xx.x)	xx.x (xx.x to xx.x)	x.xxx
Mortality at 60 days in patients with ARDS defined by the complete data-set using latent class analysis					
Alive	N (xx.x%)	N (xx.x%)	xx.x (xx.x to xx.x)		

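### Two subgroup tables compare time to extubation only among patients intubated after enrolment, while their sister tables leave the row out

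*Supplement*

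**What the plan says.** - **Definition of time to extubation (SAP section 4).** The interval runs "From date of intubation to extubation, or from the date of ICU admission to successful extubation" if the tube was placed before ICU admission. Extubation itself is "First time being successfully free from an endotracheal tube or a tracheostomy tube for 48 hours". No value is assigned to a patient who is never intubated.
- **Analysis (section 8.5).** The plan specifies "Time to extubation, mean (SD) by phenotype, difference in means (95% CI") with a t-test or Mann-Whitney test, and an ANCOVA on baseline covariates. It states no denominator and no rule for patients without a value.
- **Population (section 1).** Patients on CPAP or HFNO are eligible, so some enrolled patients may never be intubated.
- **Tables (Appendix 1).** The main table for "patients receiving high-flow nasal oxygen at a rate of at least 30 litres per minute" has a time-to-extubation row. So does "Table x.x.x Secondary analyses, non-invasive ventilation cohort", which uses the LCA phenotype. The table headed "Sensitivity analysis of the main clinical outcomes, patients receiving high-flow nasal oxygen" (any flow rate) has none.
- **Duration of ventilation (section 4).** This has a different start: "From the date of commencing ventilatory support, or the date of ICU admission" if support began earlier. The entry on unassisted breathing counts pressure support by NIV as ventilatory support and CPAP without pressure support as unassisted. It does not classify HFNO.

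**The concern.** In a cohort on HFNO or NIV, a tube time exists only after a later intubation. Section 2.2 lists intubation rate in HFNO patients as a secondary outcome, to be compared between phenotypes. A tube-time comparison in such a cohort therefore sets two groups side by side that were selected by an outcome. Any difference mixes the effect of phenotype on tube time with the effect of phenotype on who is intubated. Covariates measured at baseline do not remove a selection that happens afterwards.

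At stake is a mean difference and a p-value in a published subgroup table that a reader would take as a statement about recovery in that cohort. The never-intubated patients would not be in it.

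**Working it through.** **1. The six tables side by side (time-to-extubation row).**

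| Cohort | Main table | LCA table |
|---|---|---|
| NIV | absent | present |
| HFNO, any flow | absent | absent |
| HFNO, at least 30 L/min | present | absent |

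The 30 L/min cohort is a subset of the any-flow cohort, so there is no evident reason for it to carry a row that its parent omits. Intubation rate, ventilator-free days and duration of ventilation appear in all six.

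**2. Who has a value.** Take the cohorts as defined by support at enrolment. The plan does not say this; it is an assumption. In the two tables marked present, a patient then contributes only if intubated after enrolment.

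**3. Can this distort, and which way?** The plan has no figure to reproduce: it gives no intubation rate and no tube time. All inputs here are assumed. Severity u is normal with SD 1 and mean 0 in the hypo-inflammatory group and m in the hyper-inflammatory group. Patients above a severity threshold are intubated. Log tube time is log 8 + b·u plus noise of SD 0.5, with no direct phenotype effect and no deaths. If a proportion p is intubated and t is the standard normal value exceeded with probability p, then

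mean tube time among the intubated = 8 · exp(b·m + b²/2 + 0.125) · Φ(b − t) / p.

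For b = 0.3 and m = 0:
- hypo, p = 0.20, t = 0.842: 9.48 × 0.294 / 0.20 = 13.9 days
- hyper, p = 0.45, t = 0.126: 9.48 × 0.569 / 0.45 = 12.0 days

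A severity shift m multiplies the hyper mean by exp(b·m). Intubation is held at 20% v 45%:

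| Scenario for hyper | b = 0.3, hyper v hypo | b = 0.5, hyper v hypo |
|---|---|---|
| Same severity, lower threshold (m = 0) | 12.0 v 13.9 | 14.7 v 18.8 |
| 0.3 SD sicker, somewhat lower threshold | 13.1 v 13.9 | 17.1 v 18.8 |
| 0.5 SD sicker | 13.9 v 13.9 | 18.9 v 18.8 |
| Sicker, common threshold (m = 0.842 − 0.126 = 0.72) | 14.9 v 13.9 | 21.1 v 18.8 |

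So hyper looks faster by 1.9 to 4.1 days in the first row and slower by 1.0 to 2.3 days in the last. Exchanging the phenotype labels in the first row gives the mirror image: hyper would look falsely slower. At b = 0.3 the reversal is gone once severity accounts for about 0.50 of the 0.72 SD needed to explain the whole intubation gap.

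**4. With deaths added.** A patient who dies intubated also has no extubation time. In a simulation with 50% (hyper) v 25% (hypo) intubated, b = 0.4 and a death hazard rising with severity (all assumed), mean time among those extubated was 10.5 v 11.9 days with a lower threshold for hyper, and 12.1 v 11.9 with a common threshold. The pattern is the same.

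**5. Duration of ventilation.** The clock starts at ventilatory support, not at intubation. If HFNO counts as support, every HFNO patient has a value. If it does not, only those escalated do. NIV pressure-support patients have a value without any escalation. The text does not decide between the two readings for HFNO.

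**The case against.** The strongest reply is that these are example tables, that the row is missing from four of the six, and that section 7.3 limits subgroup reporting to outcomes judged pertinent. The two rows may be template slips. That is plausible, but pertinence is not defined, and rows filled in as drawn would yield a p-value on a post-baseline subset.

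It can also be said that a separate analysis of mechanically ventilated patients is planned with its own time-to-extubation row, that an adjusted analysis exists, and that intubation rate and ventilator-free days stand in the same tables. This softens the problem. It does not repair the two rows, and the plan does not say whether the mechanically ventilated subgroup is defined at enrolment.

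The reply is right on two stronger readings that a reader might infer:
- **That the more often intubated phenotype will look as if it recovers faster.** The documents do not support this. It needs that phenotype to be intubated at lower severity. The study's own hypothesis is that hyper-inflammatory patients do worse (32% v 17% mortality assumed), and with a common threshold there is no reversal.
- **That duration of ventilation has the same defect.** This is not established, because HFNO is unclassified and the clock does not start at intubation.

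**Conclusion.** The point holds for time to extubation in two tables: the main table for HFNO of at least 30 L/min and the LCA table for NIV. There the comparison is conditional on a post-baseline event that is itself an outcome, and it contradicts the layout of the sister tables. The same conditioning touches the main ARDS table, which combines patients intubated at enrolment with those intubated later and has no value for the never-intubated.

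Neither direction nor size can be read from the documents. The illustrative range of 4.1 days too fast to 2.3 days slower rests wholly on assumed intubation rates, tube times and severity thresholds. It shows only that the sign depends on how patients come to be intubated. The conclusion also assumes that the cohorts are defined by support at enrolment.

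For duration of ventilation, what stands is an undefined denominator in the HFNO tables. The primary outcome, 60-day mortality, is untouched. The matter is worth correcting before analysis because the correction is small.

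**What to change.** 1. Delete the time-to-extubation row from the main table for HFNO of at least 30 L/min and from the LCA table for the NIV cohort. Rely there on intubation rate and ventilator-free days.
2. In the main ARDS table and section 8.5, report time to extubation for patients intubated at enrolment, and print the denominator. The cost is fewer patients in that row.
3. Reconcile the section 4 entries on unassisted breathing and duration of ventilation as to whether HFNO counts as ventilatory support. If it does not, drop duration of ventilation from the HFNO tables in favour of ventilator-free days.
4. Do not score never-ventilated patients as 0 days of ventilation. An HFNO patient who dies without being ventilated would then receive the best possible value. Ventilator-free days avoid this, since death before day 28 scores zero. Their section 4 entry counts to day 28 from the start of ventilatory support in one place and from enrolment in another. It needs the same clarification so that every patient has a value.

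This is SAP wording and two deleted rows; no new data are needed.
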